## 5.2 Pre-Treatment Criteria

Prior to any study related testing, patients will sign the informed consent form and undergo medical evaluation to establish their baseline condition and determine eligibility. Imaging and all other studies will be obtained within 28 days of enrollment for the purpose of baseline assessment:

- Complete medical history and physical examination including:
- Complete medical history
- Documentation of disease status
- Documentation of prior systemic therapies for advanced disease treatment
- Documentation of current medications and all medications used within 30 days prior to enrollment.
- Complete physical examination, including vital signs (pulse, blood pressure, weight, and height) and assessment of ECOG performance status (See Appendix A)
- Pre-existing conditions will be assessed and evaluated according to the NCI CTCAE v4.0 to establish the patient's baseline condition

The following screening laboratory tests will be performed within 28 days prior to Day 1 of treatment:

- CBC with differential
- Chemistries: sodium, potassium, calcium, magnesium, glucose, creatinine, total bilirubin alkaline phosphatase [ALP], aspartate transaminase [AST], alanine transaminase [ALT], urea or blood urea nitrogen [BUN], total protein, albumin

- Urinalysis
- Urine or serum pregnancy test (for premenopausal women)
- ECG

Disease-specific testing:

- Baseline CT scans of the chest, abdomen and pelvis and baseline imaging of the brain by MRI (or CT with contrast if MRI is contraindicated.) Repeat tumor assessments (CT chest, abdomen and pelvis) will be performed every 8 weeks thereafter to assess response and disease progression. Brain imaging (MRI, or CT with contrast in patients with contraindications to MRI) should be obtained every 8 weeks for patients with known brain metastases at the start of treatment. For patients without known history of brain metastases, CNS imaging should be obtained if clinically indicated based on symptoms.
- Mandatory pre-treatment tumor biopsy will be obtained within 28 days of Cycle 1, Day 1. Processing of tumor biopsy specimens will be performed as outlined in section 8.3.1.1

## 5.2.1 Cycle 1, Day 1

Patients who have signed the informed consent form, completed the screening process, and met the criteria for enrollment will be entered into the trial and assigned an identification number. In addition the following will be performed:

- Certification that patient meets all inclusion and exclusion criteria and is able to comply with all requirements of the clinical trial
- Review concomitant medications since screening
- Perform physical examination with vital signs and ECOG performance status
- Blood investigations to be done if screening labs were done more than 7 days prior to day 1.
- Blood investigations performed on C1D1 must be reviewed before starting treatment to ensure that there are no clinically significant abnormalities. However, C1D1 laboratory studies do not have to re-meet eligibility criteria to begin treatment.
- Blood for correlative ctDNA analyses

## 5.2.2 Subsequent Cycles

The following studies will be obtained at the start of each new treatment cycle:

- Complete medical history
- Complete physical examination, including vital signs (pulse, blood pressure, weight, and height) and assessment of ECOG performance status (See Appendix A)
- Documentation of all current medications
- Laboratory studies including:
  - CBC with differential
  - Chemistries: sodium, potassium, calcium, magnesium, glucose, creatinine, total bilirubin alkaline phosphatase [ALP], aspartate transaminase [AST], alanine transaminase [ALT], urea or blood urea nitrogen [BUN], total protein, albumin

Blood for correlative ctDNA analyses will be collected at baseline, on C1D3, C1D8, C1D15 and at the start of each new cycle.

Before beginning each cycle, any treatment related toxicities requiring treatment delay must have resolved to grade 1 or pre-therapy baseline. If toxicities have not resolved to grade 1 on the scheduled day of retreatment, treatment may be delayed for up to 28 days from the time of the last daily dose of EGF816 and gefitinib.

For patients who require drug holds to manage toxicities, the cycle day count should continue during the hold and the dosing and assessment schedule should not change.

#### 5.3 Agent Administration

#### 5.3.1 EGF816

Investigational Product: EGF816 Pharmaceutical Form: Tablets Source: Novartis Procurement: Provided via sponsor, dispensed from research pharmacy. Unit Strength: 150mg tablets Daily Dose: 100 mg once daily Duration of Use: Continuous daily dosing without interruption Administration Route: Oral (swallowed) Schedule: Once daily, with or without food

Missed Doses/Vomited Doses: If a patient inadvertently does not take the EGF816 dose at their usual time, he or she may take the dose up to 6 hours later; in other words, they may continue as long as it is at least 6 hours before the next dose of gefitinib is due to be taken. The daily treatment schedule will be resumed the next day with the patient taking the scheduled dose at the usual time. If an entire daily dose is skipped, the patient should resume treatment the following day with their regular dose. No "make-up dose" or increased dosing should occur. If a dose is vomited within 1 hour of administration, medications to control nausea and vomiting should be used, and the dose can be repeated. Patients should report all vomited, missed or delayed doses to the study staff and will be provided with a medication diary which should be turned in at every visit (see appendix 5.)

Tablets should be swallowed whole and not chewed or opened. Patients should be instructed to take their dose of each drug at approximately the same time of day. Drugs should be separated by approximately 12 hours (e.g, gefitinib taken in the morning and EGF816 in the evening.) The time of drug administration should be recorded by the patient in the study-provided drug diary. On days when blood for PK samples need to be collected in clinic, the patient should hold their morning gefitinib until arrival, and take the dose in the clinic after clearance to do so from the care team.

Grapefruit or grapefruit juice, seville orange (and juice), pummelos, star citrus fruits and hybrids of these mentioned fruits should be avoided during study treatment.

## 5.3.2 Gefitinib

Commercial Product: Gefitinib Pharmaceutical Form: Tablets Source: Commercial pharmacy Procurement: Obtained directly from commercial pharmacy, delivered to patient. Unit Strength: 250 mg tablets Daily Dose: 250 mg once daily Duration of Use: Continuous daily dosing without interruption Administration Route: Oral (swallowed) Schedule: Once daily, with or without food

If a patient inadvertently does not take the gefitinib dose at their usual time, he or she may take the dose up to 6 hours later, in other words, they may continue as long as it is at least 6 hours before the next dose of EGF816 is due to be taken. The daily treatment schedule will be resumed the next day with the patient taking the scheduled dose at the usual time. If an entire daily dose is skipped, the patient should resume treatment the following day with their regular dose. No "make-up dose" or increased dosing should occur. If a dose is vomited within 1 hour of administration, medications to control nausea and vomiting should be used, and the dose can be repeated. Patients should report all vomited, missed or delayed doses to the study staff and will be provided with a medication diary which should be turned in at every visit (see appendix 5.)

Tablets should be swallowed whole and not chewed or opened. However, gefitinib may be dissolved in 4-8 oz of water if patients have difficulty swallowing the tablets. **Drugs should be separated by 12 hours (e.g, gefitnib taken in the morning and EGF816 in the evening.)** Patients should be instructed to take their dose of each drug consistently at approximately the same time each day. Time of drug administration should be recorded by

the patient in the study-provided drug diary. On days when blood for PK samples need to be collected, the patient should take the dose in the clinic.

## 5.4 General Concomitant Medication and Supportive Care Guidelines

Information about concomitant medications will be collected as part of this study. This will be collected during screening, at the start of each cycle, and at the time of study discontinuation. Patients are allowed to receive full supportive care therapies concomitantly during the study. No other chemotherapy, immunotherapy, hormonal cancer therapy or experimental medications will be permitted while the patients are receiving study therapy.

5.4.1 Permitted Concomitant Therapy

In general, concomitant medications and therapies deemed necessary for the supportive care (e.g., such as anti-emetics, anti-diarrhea) and safety of the patient are allowed. Anticoagulation treatment is also allowed if INR has been established within the therapeutic range prior to study entry. PT and PTT  $\geq 1.5x$  ULN are permitted in these cases. The patient must be told to notify the investigational site about any new medications he/she takes after the start of the study treatment. All medications (other than study treatment) and significant non-drug therapies (including physical therapy, herbal/natural medications and blood transfusions) administered within 28 days prior to the administration of study treatment and during the study must be listed on the Prior and Concomitant Medications or the Surgical and Medical procedures eCRF.

Patients who develop a solitary site of disease progression may undergo locally ablative therapy (LAT; including radiotherapy, ablation or surgical resection) to the site of progression and remain on study. Note that if the solitary site of progression is within a target lesion, the tumor response will be categorized as progression at the time LAT begins. EGF816 and gefitinib should be held for at least 5 days prior to LAT. EGF816 and gefitinib may be resumed >3 days after completing local therapy if all procedure related toxicities have resolved to  $\leq$  Grade 1. No other concomitant anti-neoplastic therapy will be allowed.

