#### 11.2 Response Criteria

#### 11.2.1 Evaluation of Target Lesions

Complete Response (CR): Disappearance of all target lesions. Any pathological lymph nodes (whether target or non-target) must have reduction in short axis to <10 mm.

Partial Response (PR): At least a 30% decrease in the sum of the diameters of target lesions, taking as reference the baseline sum diameters.

Progressive Disease (PD): At least a 20% increase in the sum of the diameters of target lesions, taking as reference the smallest sum on study (this includes the baseline sum if that is the smallest on study). In addition to the relative increase of 20%, the sum must also demonstrate an absolute increase of at least 5 mm. (Note: the appearance of one or more new lesions is also considered progressions).

Stable Disease (SD): Neither sufficient shrinkage to qualify for PR nor sufficient increase to qualify for PD, taking as reference the smallest sum diameters while on study.

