#### 11.2.3 Evaluation of New Lesions

The finding of a new lesion should be unequivocal (i.e. not due to difference in scanning technique, imaging modality, or findings thought to represent something other than tumor (for example, some 'new' bone lesions may be simply healing or

flare of pre-existing lesions). However, a lesion identified on a follow-up scan in an anatomical location that was not scanned at baseline is considered new and will indicate PD. If a new lesion is equivocal (because of small size etc.), follow-up evaluation will clarify if it truly represents new disease and if PD is confirmed, progression should be declared using the date of the initial scan on which the lesion was discovered.

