#### 11.2.5 Duration of Response

Duration of overall response: The duration of overall response is measured from the time measurement criteria are met for CR or PR (whichever is first recorded) until the first date that recurrent or progressive disease is objectively documented (taking as reference for progressive disease the smallest measurements recorded since the treatment started, or death due to any cause. Participants without events reported are censored at the last disease evaluation).

Duration of overall complete response: The duration of overall CR is measured from the time measurement criteria are first met for CR until the first date that progressive disease is objectively documented, or death due to any cause. Participants without events reported are censored at the last disease evaluation.

Duration of stable disease: Stable disease is measured from the start of the treatment until the criteria for progression are met, taking as reference the smallest measurements recorded since the treatment started, including the baseline measurements.

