## 11.2.6 Progression-Free Survival

Progression-Free Survival (PFS) is defined as the time from randomization (or registration) to the earlier of progression or death due to any cause. Participants alive without disease progression are censored at date of last disease evaluation.

Overall Survival: Overall Survival (OS) is defined as the time from randomization (or registration) to death due to any cause, or censored at date last known alive.

Progression-Free Survival: Progression-Free Survival (PFS) is defined as the time from randomization (or registration) to the earlier of progression or death due to any cause. Participants alive without disease progression are censored at date of last disease evaluation.

Time to Progression: Time to Progression (TTP) is defined as the time from randomization (or registration) to progression, or censored at date of last disease evaluation for those without progression reported.

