## 13.5 Interim Monitoring Plan- N/A

## **13.6** Analysis of Primary Endpoints

The primary end-point is proportion of patients free from objective disease progression or death at 9 months. Progression will be defined by RECIST 1.1

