# 13.7 Analysis of Secondary Endpoints

Response rate will be assessed as per RECIST, see Section 9.1. Results will be reported with 95% confidence intervals. All patients will be evaluable for response rate. Progression-Free Survival (PFS) will be defined as the duration of time from start of treatment to time of objective disease progression or death. Overall survival (OS) will be defined as the duration of time from start of treatment until death. Analysis will be performed using the Kaplan-Meier method. All patients will be evaluable for survival endpoints.

A summary of the adverse events, grading according to CTCAE and their attributed relatedness to treatment will be provided as a measure of patient safety and tolerability. All patients will be included in the safety analyses.

The first six patients in the study will constitute a safety cohort as outlined in section 5.1. If >1 patient has a grade 3 or higher treatment-related adverse event during cycle 1 of treatment, the dose will be de-escalated as outlined. Six additional patients will be treated at the lower dose to establish safety prior to proceeding to open enrolment of the remainder of the trial. The probability of stopping at the initial dose in order to dose de-escalate and the probability of stopping the trial after the safety run in at the lower dose based on assumptions about the associated underlying toxicity rates are as follows:

True toxicity rate	Probability of reducing the starting dose	Probability of stopping the trial
0.05	0.265	0.033
0.1	0.468	0.114
0.2	0.738	0.345
0.3	0.883	0.580
0.4	0.954	0.767
0.5	0.985	0.890

Biopsies from pre, post and on-treatment will be obtained to facilitate comparative analysis by next-generation sequencing, single-cell RNA sequencing, transcriptional profiling and an evaluation of the emergent resistance mechanisms at the time of progression. Analyses for these outcomes may include the Cox proportional Hazard models for the examination of the relationship between changes in sequencing parameters and time to progression, Sign-Rank test to compare pre and post measurements of gene expression for genes of interest and other correlation tests such as linear regression to examine relationship between relevant outcomes.

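### Does the local-ablation note in Section 5.4.1 leave the progression date for PFS and the 9-month endpoint undefined?

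*Combined protocol and SAP*

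**What the plan says.** The note in Section 5.4.1 concerns a solitary progression inside a target lesion: "if the solitary site of progression is within a target lesion, the tumor response will be categorized as progression at the time LAT begins". The next sentence adds that "EGF816 and gefitinib should be held for at least 5 days prior to LAT".

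The endpoint definitions are elsewhere:

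- Section 13.6 sets the primary endpoint as the proportion free of objective progression or death at 9 months (39 weeks in Section 1.2) and states "Progression will be defined by RECIST 1.1".
- Section 13.7 has PFS "defined as the duration of time from start of treatment to time of objective disease progression or death".
- Section 11.2.6 ends PFS at "the earlier of progression or death due to any cause", without a dating rule.
- Section 11.2.3 says of a new lesion that is equivocal at first and later confirmed that "progression should be declared using the date of the initial scan on which the lesion was discovered".
- Section 11.2.5 runs duration of response to "the first date that recurrent or progressive disease is objectively documented".
- Section 11.2.1 requires, for target-lesion progression, a rise of at least 20% and at least 5 mm in the sum of diameters over its smallest value. It adds that "the appearance of one or more new lesions is also considered progressions".

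None of these endpoint passages mentions LAT.

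**The concern.** Read literally, the note dates a progression by the start of a procedure, while the rest of the plan dates it by imaging. If a scan has already met RECIST progression, the LAT date comes later. The delay is at least 5 days when the drug hold follows the scan. Two analysts could then record different PFS times for the same patient.

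The trial has one arm, so no control group would absorb the delay, and it would favour the combination. Median PFS is a secondary objective. The primary analysis counts patients progression-free at 9 months against fixed cut-offs (7 of 11, then 23 of 36), so any patient moved across the landmark would matter.

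**Working it through.** **1. Which texts actually conflict.** Section 11.2.3 deals with equivocal new lesions, and the note deals with target lesions. Section 11.2.5 defines duration of response. Section 13.6 gives a criterion, not a date. A solitary new lesion is progression under Section 11.2.1 whether or not LAT is given. That leaves Section 13.7, which ends PFS at objective progression. Starting LAT is not an objective measurement, so when a scan has met RECIST progression, Section 13.7 points to the scan. The note itself speaks of how the response is categorised and sits among the concomitant-therapy rules.

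**2. The note can also act the other way.** Target progression depends on the sum of up to five lesions. Illustration with assumed sizes: smallest sum 120 mm, one lesion growing from 20 to 35 mm. The rise is 15/120 = 12.5%, below 20%, so this is not RECIST progression. If that lesion is treated, the note records an event that RECIST would not. So it is not true that the note can only delay events.

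**3. Can the 9-month count change?** Inputs: scans every 8 weeks in year 1 (Table 10-1, note e), a window of 3 days either side (Section 10), landmark at week 39. Days are counted from the start of treatment.

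- Landmark: 39 × 7 = day 273.
- Week-32 scan: 224 ± 3 = days 221 to 227. Time left to the landmark: 273 − 227 = 46 to 273 − 221 = 52 days.
- Week-40 scan: no earlier than 280 − 3 = day 277, after the landmark under either dating rule.

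For a progression seen on a scheduled scan, the two dates give different 9-month status only if LAT starts more than 46 to 52 days after the week-32 scan. Progression on an earlier scan would need a longer gap. The other route is an unscheduled scan shortly before day 273 (within 5 days of it, at the minimum gap).

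**4. The plan's own design figures.** The probability of rejecting the null is the sum over x = 7 to 11 of C(11,x) pˣ(1−p)¹¹⁻ˣ × P[Bin(25,p) ≥ 23−x].

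- p = 0.50: 0.0479, against a stated limit of 0.05.
- p = 0.73: 0.8106, against a stated 80%.

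The stated design reproduces. If a share m of patients who fail by 9 months were wrongly counted as progression-free, p = 0.50 becomes 0.50 + 0.50m. Type I error would then be 0.0538, 0.0604 or 0.0836 for m = 1%, 2% or 5%. Misclassification would therefore matter if it happened, but step 3 shows how narrow the route to it is.

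**5. Median PFS if the LAT date is used.** The documents give neither an LAT frequency nor a scan-to-LAT gap, so both are assumed. Simulation: 20,000 trials of 36 patients, no censoring, exponential progression times with a 9-month median, detection at scans every 56 days to day 336 and every 84 days after, each ± 3 days. A share of events is moved later by a fixed gap. Mean rise in the Kaplan-Meier median, in days:

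| Gap | 5% of events | 10% | 20% |
|---|---|---|---|
| 5 days | 0.26 | 0.51 | 1.03 |
| 14 days | 0.75 | 1.49 | 2.82 |
| 28 days | 1.49 | 2.99 | 5.80 |

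These are close to share × gap (0.05 × 5 = 0.25; 0.20 × 28 = 5.6). With a 19.8-month median, which corresponds to 73% progression-free at 9 months, the range is 0.26 to 5.79 days. The proportion progression-free at day 273 changed by 0.000 in all 18 scenarios. Step 3 implies this, because the longest assumed gap (28 days) is shorter than 46 days. The simulation has no unscheduled scans and only moves events later, so it leaves out the case in step 2.

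**The case for a change.** The strongest case for amending is that no sentence says whether the specific note displaces the general wording of Section 13.7, so either date could be defended. Where a qualifying scan comes first, the literal reading can only lengthen PFS. In a single trial the median could move by the whole gap if the median event is an affected one. LAT also alters the lesion whose diameter would define later progression, which is a reason to settle the date in advance. One sentence would be cheap.

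The missing cross-reference stands, and so does the direction of the shift in that case. The claim that PFS has no stated end does not stand, because Section 13.7 supplies one. Nor does a one-way bias, because of the sub-threshold case.

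The obvious remedy is to replace the note with a rule counting only progression that meets RECIST 1.1. That would stop counting the patient in step 2 at the start of LAT. The treated lesion may then shrink or leave the sum, so a later RECIST event could be delayed or missed. The replacement could create the upward bias it was meant to remove.

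**Conclusion.** No change is needed. The plan lacks a cross-reference, but an analyst following Section 13 will date the event by the scan that first meets RECIST 1.1 progression. Where none has, the note still counts the patient as progressed when LAT starts. Taking the earlier of the two dates respects both texts and is conservative.

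Even the less favourable literal reading leaves 9-month status unchanged for progression on scheduled scans unless LAT follows the week-32 scan by more than 46 to 52 days. It adds on average 0.3 to 5.8 days to a descriptive median of about 9 months, with scans 56 days apart. The design's type I error (0.0479) and power (0.8106) are untouched when Section 13 is followed. The shift in the median rests on assumed LAT shares (5 to 20%) and gaps (5 to 28 days). More frequent LAT or longer gaps would raise it roughly in proportion. An unscheduled scan just before day 273 remains a possible exception.
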